11.1 Screening Failures

Subjects who sign and date the ICF and assent (if applicable) but who fail to meet the inclusion and exclusion criteria are defined as screen failures. A screening log, which documents the subject's initials and reason(s) for screen failure, is to be maintained by the Investigator for all screen failures. A copy of the log should be retained in the Investigator's study files. Screen failures will not be added to the eCRF.

11.2 Discontinuation from Study Drug

A subject may have study drug prematurely discontinued for any of the following reasons:

- Safety, including AEs or development of clinically significant laboratory abnormalities. The subject must be followed clinically until the event is resolved or deemed stable.
- Clinical failure or lack of efficacy.
- Subject wishes to withdraw consent for reasons other than an adverse experience.
- Subject non-compliance or unwillingness to comply with the procedures required by the protocol.
- Investigator discretion.
- Sponsor request.

Any subject who prematurely discontinues study drug should be encouraged to complete the study through the last study visit. The Last Day of Treatment procedures will be performed the day (+48 hours) the study drug is discontinued.

11.3 Withdrawal from Study

A subject may be withdrawn from the study for any of the following reasons:

- Subject wishes to withdraw consent for reasons other than an adverse experience
- Subject wishes to withdraw consent due to an adverse experience
- Subject is lost to follow-up
- Subject non-compliance or unwillingness to comply with the procedures required by the protocol
- Investigator discretion
- Sponsor request

11.4 Study Site Discontinuation

Reasons for discontinuation of the study at an investigational site may include, but are not limited to, the following:

- The incidence or severity of AEs in this or other studies indicates a potential health hazard to subjects
- Subject enrollment is unsatisfactory
- Investigator request to withdraw from participation
- Sponsor decision
- Serious and/or persistent non-compliance by the investigator with the protocol, the clinical research agreement, and/or applicable regulatory guidelines in conducting the study
- Institutional review board (IRB)/independent ethics committee (IEC) decision to terminate or suspend approval for the investigation or the investigator
- Investigator fraud (altered data, omitted data, or manufactured data)
- Recommendation from the DMC

12 SAFETY ASSESSMENTS

Safety assessments will include attention to relevant changes in physical examinations, clinical condition, vital signs, and safety laboratory tests that are identified as occurring after the ICF and assent (if applicable) are signed regardless of relationship to study drug. Any study team member may conduct safety assessments.

12.1 Adverse Events

An AE is any untoward medical occurrence associated with the use of a study drug in humans, whether or not considered drug related. An AE can be a clinical event in the form of signs, symptoms, disease, or laboratory or physiological observations occurring in a human being participating in a clinical study with study drug or comparator, regardless of causal relationship. A “pre-existing” condition is one that is present prior to study drug administration and is reported as part of the subject’s medical history. A pre-existing condition should be reported as an AE only if the frequency, intensity, or character of the pre-existing condition worsens during the course of the study.

Laboratory abnormalities are not considered AEs unless they are associated with clinical signs or symptoms, or require medical intervention. However, a clinically significant laboratory abnormality (e.g. detected on clinical chemistry or hematology) that is independent from the underlying medical condition and that requires medical or surgical intervention, or leads to study drug interruption or discontinuation, will usually be considered an AE.

Lack of efficacy/clinical failure is captured as an efficacy measure and in general will not be considered an AE.

Adverse events will be collected from the time of signing of the informed consent until 28 days post-randomization. In addition, the investigator (or designee) should seek to elicit any clinical or objective reactions by specific questioning (“How have you been feeling?”) and, as appropriate, by examination. Information on all AEs should be recorded on the eCRF. All clearly related signs, symptoms, and results of diagnostic procedures performed because of an AE should be grouped together and recorded as a single diagnosis. The component parts of the diagnosis may be listed for verification. If the AE is a laboratory abnormality that is part of a clinical condition or syndrome, it should be recorded as the syndrome or diagnosis rather than the individual laboratory abnormality.

To avoid vague, ambiguous, or colloquial expressions, all AEs should be recorded in standard medical terminology on the eCRF and on the medical record rather than in the subject’s own words. Each AE will also be described in terms of duration (start and stop date and times), severity, association with the study drug, action(s) taken, and outcome.

12.1.1 Serious Adverse Events

An AE or suspected adverse reaction is considered serious if, in the view of the investigator or sponsor, it results in any of the following outcomes:

- Death: “Death” is an outcome and is NOT the AE. In the event of death, the cause of death should be recorded as the AE. The only exception is “sudden death” when the cause is unknown.
- Life-threatening AE: Places the subject at immediate risk of death at the time of the event as it occurred. It does not include an AE that, had it occurred in a more severe form, might have caused death.
- Persistent or significant incapacity or substantial disruption of the ability to conduct normal life functions
- Subject hospitalization or prolongation of hospitalization. A “planned” hospitalization for study procedures or preexisting conditions is NOT an SAE.
- Congenital anomaly or birth defect

Important medical events that may not result in death, be life threatening, or require hospitalization may be considered an SAE when, based on appropriate medical judgment, they may jeopardize the subject and may require medical or surgical intervention to prevent one of the outcomes listed in this definition above. Examples of such medical events include allergic bronchospasm requiring intensive treatment in an emergency room or at home, blood dyscrasias that do not result in in subject hospitalization, or the development of drug dependency or drug abuse.

Serious AEs will be collected from the time of signing of informed consent until 28 (\pm 4) days after randomization. All SAEs, regardless of the investigator’s assessment of causal relationship to study drug, must be reported by the investigator or qualified designee within 24 hours of the site’s knowledge of the event, and a copy of the initial SAE report must be received within 1 business day.

The report must include an assessment of whether there is a reasonable possibility that the study drug caused the event. “Reasonable possibility” means there is evidence to suggest a causal relationship between the study drug and the AE.

12.1.2 Follow-up of SAEs

When additional relevant information becomes available, the investigator will record follow-up information according to the same process used for reporting the initial event as described above. The investigator will follow all SAEs until resolution, stabilization, or the event is otherwise explained.

All SAEs will be followed until resolution, stabilization, until otherwise explained, or until the last subject completes the final follow-up, whichever occurs first.

12.1.3 Other Reportable Events

Reports of overdose (with or without an AE), inadvertent or accidental exposure, and known pregnancy should be forwarded in the same time frame as an SAE.

Overdose occurs when a subject is administered or has taken a dose greater than the intended or scheduled dose specified by the protocol.

All pregnancies occurring during the study must be followed for information regarding the course of pregnancy, delivery, and condition of the newborn. Follow-up should be provided by the investigator to the medical monitor in a timely manner.

Monitoring of liver laboratory tests

Monitoring of liver laboratory tests of special interest (AST, ALT, and direct bilirubin) will be conducted throughout the study. Three levels of monitoring will be performed:

Weekly monitoring: Each week, data entered in the eCRF will be downloaded to identify any child enrolled in the study with a) normal AST, ALT, or direct bilirubin at baseline AND at least $2 \times \text{ULN}$ on any of these laboratory tests at any study visit post baseline and b) any child meeting laboratory criteria for Hy's Law. These data will be provided to the DCRI medical monitor and the sponsor for review.

Quarterly monitoring: Each quarter, summary data of children enrolled in the study with a) normal AST, ALT, or direct bilirubin at baseline AND at least $3 \times \text{ULN}$ on any of these laboratory tests at any study visit post baseline and b) any child meeting laboratory criteria for Hy's Law will be provided to the DMC chair for review. Actions by the DMC chair will be described in the DMC meeting minutes.

Biannual monitoring: Twice per year, all data pertaining to liver laboratory tests will be presented to the DMC for review. This includes the data presented quarterly as well as listings of all laboratory tests at every visit.

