In the Phase 3 IV to oral CABP study, 5 (1.2%) patients in the solithromycin group and 7 (1.6%) patients in the moxifloxacin group died during the study. None of the SAEs resulting in death was considered related to study drug. A total of 30 (6.9%) patients in the solithromycin group and 23 (5.4%) patients in the moxifloxacin group reported at least 1 non-fatal SAE. Only 3 SAEs were considered related to study drug by the investigators (urticaria and anaphylactic reaction in 1 patient each in solithromycin and anaphylactic reaction in 1 moxifloxacin patient). The most frequently reported infusion site related TEAEs were infusion site pain (10.4%), infusion site phlebitis (10.0%) and infusion related reaction (6.5%). Infusion site related TEAEs were mostly mild or moderate in intensity and infrequently led to discontinuation of study drug or withdrawal from the study (in 1 moxifloxacin and 10 solithromycin patients). Apart from infusion site related events, the most common AEs observed in patients receiving solithromycin were diarrhea (5.9%) and headache (4.2%).

In the adolescent oral phase 1 study (CE01-119), 12 AEs were reported, of which 9, including 1 SAE (limb abscess), were unrelated to solithromycin. Three subjects had AEs related to study drug: 2 separate episodes of mild headache and 1 episode of increased transaminases ($<3\times$ ULN).

The most common AEs reported after multiple IV doses were general disorders and administrative site conditions (infusion-related pain) followed by nervous system disorders and vascular disorders (phlebitis), with the majority mild in severity.

Solithromycin, like most antibiotics and like all macrolide antibiotics, has been associated with hepatic aminotransferase elevations. In the pooled Phase 3 CABP trials, ALT elevations to $>3\times\text{ULN}$, $>5\times\text{ULN}$ and $>10\times\text{ULN}$ were seen in 7.2%, 2.4% and 0.1% of solithromycin recipients compared to 3.6%, 1.0% and 0.2% of moxifloxacin recipients. Elevations of ALT to $>3\times\text{ULN}$ were 5.4% in the oral study and 9.1% in the IV to oral study. These elevations were typically asymptomatic, not associated with bilirubin elevation and readily reversible, with improvement in many cases seen during continued dosing. There have been no Hy's Law cases.

Multiple lines of evidence point to an exposure-response relationship for ALT elevation with solithromycin.

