8.2 Exclusion Criteria

1. Confirmed or suspected respiratory-tract infection attributable to sources other than community-acquired bacterial pathogens (e.g., ventilator-associated pneumonia; hospital-acquired pneumonia).
2. Received > 48 hours of potentially effective systemic antibacterial therapy for CABP immediately prior to randomization (exception: clinical or microbiological treatment failure or progression of signs or symptoms of CABP as determined by the investigator).
3. Confirmed or suspected bacterial meningitis.
4. Known active tuberculosis.
5. Non-infectious causes of pulmonary infiltrates (e.g., cystic fibrosis, chemical pneumonitis from aspiration, hypersensitivity pneumonia).
6. Evidence or history of clinically significant medical condition that may, in the assessment of the investigator, impair study participation or pose a significant safety risk or diminish the subject's ability to undergo all study procedures and assessments.
7. Hepatic dysfunction evidenced by ALT or AST > 3 times ULN or direct bilirubin greater than 2 times ULN (if direct bilirubin values are not available in a time frame consistent with enrollment requirements, total bilirubin must be < 2 times ULN).
8. Treatment with the following drugs within 72 hours prior to first dose of study drug or expected to receive these drugs during the treatment phase: drugs that potently inhibit CYP3A4 (nefazodone, fluconazole, ketoconazole, conivaptan, diltiazem, verapamil, aprepitant, imatinib, protease inhibitors, clarithromycin, ciprofloxacin, erythromycin, itraconazole, mibefradil, posaconazole, telithromycin, and voriconazole); CYP3A4 inducers (rifampin, rifabutin, phenytoin, fosphenytoin, carbamazepine, phenobarbital, rufinamide, modafinil, armodafinil, etravirine, efavirenz, nevirapine, rilpivirine, bosentan, troglitazone, pioglitazone,

and St. John's wort). In addition, the following drugs may not be co-administered with solithromycin in this trial due to the potential for adverse drug-drug interaction: digoxin, colchicine, midazolam, quinidine, ergotamine, dihydroergotamine, rivaroxaban, apixaban, dabigatran, edoxaban, cisapride, cyclosporine, sildenafil, astemizole, and alfentanil.

9. Breast-feeding females.
10. Positive pregnancy test in females of childbearing potential.
11. History of anaphylaxis to macrolide antibiotics.
12. Previous participation in this study.

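### The weekly and quarterly liver listings rest on an undefined normal-baseline condition, so some eligible children with raised baseline tests can go unlisted until the twice-yearly DMC review

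*Protocol*

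**What the plan says.** Protocol 12.1.3 sets three tiers of central monitoring for AST, ALT and direct bilirubin.

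- **Weekly**, to the medical monitor and the sponsor: the condition in limb (a) is worded "normal AST, ALT, or direct bilirubin at baseline AND at least", with a limit of 2 × ULN that a later value of one of the three tests must reach. Limb (b) adds every child who meets Hy's Law laboratory criteria, whatever the baseline.
- **Quarterly**, to the DMC chair: the same two limbs, with 3 × ULN in limb (a).
- **Biannual**, to the DMC: "Twice per year, all data pertaining to liver laboratory tests will be presented to the DMC for review", including "listings of all laboratory tests at every visit". This tier has no baseline condition.

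Protocol 8.2, criterion 7 (repeated in the synopsis) excludes "Hepatic dysfunction evidenced by ALT or AST > 3 times ULN or direct bilirubin greater than 2 times ULN". Children with ALT or AST above normal and up to 3 × ULN, or direct bilirubin above normal and up to 2 × ULN, can therefore enrol.

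On the background risk, Protocol 5.2.4.1 reports that in the pooled adult Phase 3 trials ALT elevations above 3, 5 and 10 × ULN "were seen in 7.2%, 2.4% and 0.1% of solithromycin recipients"; the moxifloxacin rate above 3 × ULN was 3.6%. It adds: "Multiple lines of evidence point to an exposure-response relationship for ALT elevation with solithromycin".

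**The concern.** The two faster tiers filter on a normal baseline, but eligibility does not require one. Nothing in 12.1.3 says how an eligible child with an abnormal baseline is screened. The word joining the three tests is also open: two programmers could build different queries from the same sentence and both comply.

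Limb (b) ignores baseline but is a weak backstop for this pattern. Protocol 5.2.4.1 says the adult ALT rises typically came without a bilirubin rise, and that there were no Hy's Law cases. An isolated transaminase rise would therefore seldom reach the listing that way.

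At stake is how quickly the medical monitor, the sponsor and the DMC chair see a worsening liver test in a child who started above normal, for a drug with a recognised transaminase signal.

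**Working it through.** The documents give no figure for this rule, so there is none to reproduce. The check has two parts.

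**1. Limb (a) applied to example profiles.** Values are multiples of ULN, baseline → post-baseline, with normal meaning ≤ 1. The three readings are:

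- *Same test*: the test that crosses the limit was normal at baseline.
- *All normal*: all three tests were normal at baseline.
- *Any one*: at least one of the three was normal at baseline.

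| Profile | Same test | All normal | Any one |
|---|---|---|---|
| ALT 2.5 → 8; AST and direct bilirubin stay normal | missed | missed | listed |
| ALT and AST 2 → 8; direct bilirubin normal | missed | missed | listed |
| ALT 2 → 8; AST 0.9 → 4; direct bilirubin normal | listed (through AST) | missed | listed |
| ALT and AST 2 → 8; direct bilirubin 1.5, unchanged | missed | missed | missed |
| ALT 2.5, unchanged; others normal | not listed | not listed | listed weekly, not quarterly |
| All 0.8 at baseline; ALT → 4 | listed | listed | listed |

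Apart from the unchanged ALT of 2.5, results are the same at the weekly 2 × and quarterly 3 × limits. Every baseline in the table is admissible under criterion 7. The fourth profile is missed by limb (a) under every reading. Limb (b) could still list it if Hy's Law criteria were met; 12.1.3 names those criteria without stating them.

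**2. Illustrative size.** Inputs:

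- Planned solithromycin arm: 300 (Protocol 14.1.2).
- Adult rate of ALT above 3 × ULN: 7.2% (Protocol 5.2.4.1).
- Share entering with a raised transaminase: not given; assumed 5% to 20%.

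Expected children above 3 × ULN outside limb (a) = arm size × share × rate.

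- 5%: 300 × 0.05 = 15; 15 × 0.072 = 1.08.
- 20%: 300 × 0.20 = 60; 60 × 0.072 = 4.32.

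Halving the rate to 3.6% gives a low end of 15 × 0.036 = 0.54. Doubling it to 14.4% gives a high end of 60 × 0.144 = 8.64.

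For a given share and rate these are upper bounds, because some children would be listed through another test or through limb (b). The adult rate may not carry over: children who start nearer the limit may cross it more often, which is why the doubled rate is shown.

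SAP Section 2 records termination with fewer than a quarter of 400 enrolled, that is, fewer than 100, or about 75 on solithromycin at 3:1. On the same assumptions the range is then at most 75 × 0.05 × 0.072 = 0.27 to 75 × 0.20 × 0.072 = 1.08.

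**The case against.** **The plain wording may already catch most of these children.** The sentence does not require the same test to be normal and then raised. If any one normal test suffices, a child with raised ALT and a normal AST or direct bilirubin is listed. This stands: the firm defect is an undefined rule, not a proven exclusion. It does not help the child abnormal on all three tests. Listing a stable elevation, the other effect of this reading, is not a safety failure.

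**Care does not run through the central download.** A reader might infer that the twice-yearly review is the only unfiltered one and comes too late to inform care. The documents do not support that. Tests are read at local laboratories. Protocol 10.4.1.1 has clinically significant abnormal values repeated until they settle, and the medical monitor told if they do not. Protocol 11.2 allows study drug to be stopped for laboratory abnormalities. Protocol 7.4 lets the DMC act on emergent data outside its schedule. None of these has a baseline condition. What remains is that they rest on investigator judgement or an ad hoc trigger, whereas the central listing is meant to be systematic.

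**No data are lost.** The biannual listings are unfiltered, and SAP 10.3.2 summarises extreme liver values and largest increases with no baseline filter stated. This also stands.

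**Direct bilirubin at baseline.** A reader might take criterion 7 to let children enrol with no baseline direct bilirubin at all. It is a timing allowance for enrolment. Table 1, footnote g, lists direct bilirubin without the asterisk that excuses non-collection.

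**Looking only for newly abnormal tests is a legitimate choice.** So it is, and criterion 7 does not strictly contradict 12.1.3. But the choice should be stated, with a route for the children it leaves out.

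**Conclusion.** The point holds as a gap in the timeliness of central review. Under a same-test or all-normal reading, a child whose transaminase rises from a raised but eligible baseline, with no test that was normal at baseline crossing the limit, is in neither faster listing unless Hy's Law criteria are met. Under the any-one reading the gap narrows to children abnormal on all three tests. The delay runs to the next biannual DMC review, up to about 6 months at the spacing in SAP Section 11.

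The number affected cannot be derived from the documents. At the planned size, the assumed 5–20% share and the adult 7.2% rate give at most about 1–4 solithromycin children above 3 × ULN outside limb (a). It would be wrong to count every child with a raised baseline as a missed signal: most would not worsen, and each stays screened, under the same-test reading, on any test that was normal at entry.

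This is worth changing because the repair is cheap. It is not evidence that children were left without follow-up. The DMC charter is not among the documents and may add rules.

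**What to change.** Reconcile Protocol 12.1.3 with exclusion criterion 7 so that the weekly and quarterly listings cover every enrolled child, whatever the baseline. Keep the existing 2 × and 3 × ULN listing limits. Print the baseline value and the ratio to baseline beside each flagged result, so that reviewers can tell a new rise from a stable one. This removes the ambiguity and closes the gap under all three readings.

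The cost is about one line in the query program, a matching edit to 12.1.3, and a slightly longer list that includes some stable elevations. No treatment or stopping rule is proposed. Since the SAP records that the trial has been terminated, the change matters chiefly if this monitoring scheme is reused.

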12.1.4 Severity of Adverse Events

AE severity will be graded based on the following:

- Mild:** Transient or mild discomfort; no medical intervention/therapy required
- Moderate:** Mild-to-moderate limitation in activity; some assistance may be needed; no or minimal medical intervention/therapy required
- Severe:** Marked limitation in activity; some assistance usually required; medical intervention/therapy required; hospitalizations possible

When changes in the severity of an AE occur more frequently than once a day, the maximum severity for the experience that day should be noted. If the severity assessment changes over a number of days, then those changes should be recorded separately (with distinct onset dates).

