10.2 Primary Safety and Tolerability Endpoints

Primary safety endpoints will be the proportion of subjects in the safety population experiencing a TEAE and the proportion of subjects in the safety population discontinuing study drug due to a related AE. Discontinuation from related AE counts will be created by using any discontinuation from related AE documented in the study drug discontinuation page and the AE data for a subject. The first safety endpoint will be evaluated through the Day 28 visit (28 days ± 4 days after randomization). This will be a composite of TEAEs through Day 16 visit and TESAEs through Day 28 visit. The second safety endpoint will be evaluated through the last day of study drug dosing.

For the primary safety end points, the frequency and percentage of subjects with at least one treatment emergent adverse event, and the frequency and percentage of subjects discontinuing study drug due to a related AE, will be determined. Ninety-five percent Clopper-Pearson (exact) confidence intervals will be calculated for each incidence of occurrence by treatment arm. Summaries will be calculated by treatment arm for the overall safety population, by treatment arm stratified within age group, and within age group and formulation for the solithromycin arm. Patient-level information for adverse events and subjects discontinuing study drug due to a related AE will be listed. For this analysis subjects will be grouped according to their randomized treatment arm assignment (intent-to-treat analysis).

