10.3.1 Adverse Events

AEs (as defined in section 12.1 of Protocol) will be collected from the time of signing the informed consent and assent (if applicable) through 16 days (± 4 days) after randomization. SAEs will be collected through 28 days (± 4 days) after randomization. AEs will be tabulated by using the Medical Dictionary for Regulatory Activities (MedDRA v18.1) system organ class and preferred term. The treatment emergent adverse event (TEAE) is defined as any AE that has an onset on or after the first dose of either study drug, or any pre-existing AE that increases in severity after dosing with either study drug. Adverse events will be tabulated to show the number of subjects with at least one AE, number of subjects with at least one TEAE, and the number of subjects that experienced each individual count of AEs and TEAEs (e.g., number of subjects with 2 AEs, number of subjects with 3-4 AEs, etc.). Additional summaries will be created for infusion site events as well as TEAEs excluding these infusion site events.

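### AE severity changes are recorded with new onset dates and the SAP never links them, so event counts are inflated and an improving pre-dose AE can pass as treatment-emergent

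*Protocol*

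**What the plan says.** Four provisions meet here.

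- **Collection.** Protocol 12.1: "Adverse events will be collected from the time of signing of the informed consent". AEs that start before the first dose can therefore be in the database.
- **Recording.** Protocol 12.1.4, on changes over several days: "If the severity assessment changes over a number of days, then those changes should be recorded separately (with distinct onset dates". The rule covers improvement as well as worsening. Changes within one day are reduced to that day's maximum.
- **TEAE definition.** SAP 10.3.1 has two limbs joined by *or*. Limb one is "any AE that has an onset on or after the first dose of either study drug". Limb two is "any pre-existing AE that increases in severity after dosing with either study drug".
- **Use.** The first primary safety endpoint in SAP 10.2 is "the frequency and percentage of subjects with at least one treatment emergent adverse event". SAP 10.3.1 also tabulates "the number of subjects that experienced each individual count of AEs and TEAEs", with rows such as "number of subjects with 2 AEs, number of subjects with 3-4 AEs, etc".

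Neither document says how the separate severity records of one event are joined for analysis.

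**The concern.** The SAP's definition assumes that an event keeps its first onset date, whereas the protocol's recording rule gives later severity records dates of their own. Limb two shows the mismatch. If every severity step carries a new onset, a pre-dose AE that worsens after dosing already satisfies limb one, and limb two adds nothing. Limb two has a purpose only if the original onset is preserved.

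Two results are at stake. The table of AE and TEAE counts may be counting severity steps and not events. The primary TEAE proportion may include children whose only qualifying record is the easing of something that began before any study drug.

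**Working it through.** The plan gives no figure on this point. Its sample-size tables do reproduce (for example 1 − 0.99^300 = 0.951 against the stated 0.95) and are not affected.

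**Step 1: apply the rules to two example events.**

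| Event | Records under Protocol 12.1.4 | TEAE records by limb one, unlinked | TEAEs if linked to first onset |
|---|---|---|---|
| A: moderate on Day −1, mild from Day 2 | 2 | 1 | 0 (no worsening) |
| B: mild Day 2, moderate Day 3, mild Day 5 | 3 | 3 | 1 |

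Event B puts the child in the 3–4 row of the count table when the true count is one. The child counts once in the primary TEAE endpoint either way. Event A is the only type that can change that endpoint, and only if the child has no other TEAE.

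**Step 2: size of the effect on the primary TEAE proportion.** Let a be the share of children with an AE starting between consent and first dose, h the share of those that improve after dosing, and b the true TEAE proportion. Taking b to be the same in affected and other children, the rise is (1 − b) × a × h.

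Inputs, all assumptions because the documents give none of them: a = 2–5%, h = 0.5, b = 20–50%.

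- Low: (1 − 0.50) × 0.02 × 0.5 = 0.005, or 0.5 percentage points.
- High: (1 − 0.20) × 0.05 × 0.5 = 0.020, or 2.0 percentage points.

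**Step 3: convert to children.** SAP section 2 reports enrolment below one quarter of 400, so fewer than 100. If the 3:1 allocation held (assumption), about 75 or fewer received solithromycin.

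- 0.005 × 75 = 0.4 children; 0.020 × 75 = 1.5 children.
- One misclassified child moves the proportion by 1/75 = 1.33 points, against 1/300 = 0.33 points at the planned size.

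**Step 4: compare with the precision.** The exact 95% interval for 15 of 75 is 11.6% to 30.8%, and for 38 of 75 it is 38.9% to 62.4%. A shift of 0.5 to 2.0 points is well inside either.

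**Step 5: the smallest cells.** SAP 10.2 also reports the endpoint by age group and formulation, and SAP Table 3 lists ten such solithromycin cohorts. At 75/10 = 7.5 children per cohort on average, one child moves a cohort's proportion by about 13 points.

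**The case against.** The strongest reply is that limb two is the specific provision for an AE already present at dosing and requires an increase. Protocol 12.1.4 says that the changes are recorded separately, not that each is a new AE. Reading both limbs so that each has effect, an improving pre-dose event is not a TEAE. Protocol 12.1 takes the same line for pre-existing conditions, which become AEs only if they worsen. This largely stands. A reader might infer that an improving pre-dose event is definitely a TEAE under the plan, but the documents do not settle that. They leave two limbs in conflict once the records are split, and the programmer has to choose.

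A reader might also infer that repeat records inflate the primary endpoints. They cannot. One endpoint is any TEAE per subject, and the other is discontinuation for a related AE, also per subject.

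Three further points stand:

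- The exposed group is small. The 72 hours in the schedule of assessments is how far screening may precede randomization, not a consent-to-dose interval, and screening and first dose may fall on the same day. Symptoms kept as medical history enter only if they worsen.
- The recording rule covers both arms. Improvement after dosing could differ by arm, but nothing in the documents shows that it does.
- The eCRF is not among the documents and may link the records. All AEs are listed, so with fewer than 100 children any affected case could be found.

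What the reply does not remove is the count table, where repeat counting follows directly if records are used as events, and the lack of any stated rule.

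**Conclusion.** The gap is real and minor. Without a linking rule, literal programming overstates the number of AEs and TEAEs per subject whenever severity changes over days. It can also place an improving pre-dose AE in the primary TEAE proportion, contrary to the evident intent of limb two.

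The second effect adds about 0.5 to 2.0 percentage points, or 0.4 to 1.5 of about 75 solithromycin children. That rests on the assumed 2–5% with a pre-dose AE, half of them improving, a true TEAE rate of 20–50%, and 3:1 allocation among fewer than 100 enrolled. It mainly affects each arm's absolute proportion, and the documents do not support a claim that it biases the comparison between arms. It is most visible in the small age-by-formulation cells.

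**What to change.** Add to SAP 10.3.1:

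1. Link contiguous severity-change records of the same event into one episode carrying the original onset date. Use the same preferred term with one record's stop date meeting the next onset, or an eCRF link if one exists.
2. Class an episode with pre-dose onset as a TEAE only if a post-dose severity exceeds the last pre-dose severity.
3. Report TEAE severity as the maximum over post-dose records only. A maximum over the whole episode could assign a pre-dose grade to a TEAE, for example in an event that was severe, then mild before dosing, then moderate after it.
4. Use episodes, not records, for the count table and the primary TEAE endpoint.

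The cost is a few sentences and one derivation step in the AE analysis dataset; no new data are needed. The downside is that two truly separate back-to-back events with the same term would be merged, which can be checked against the AE listing.
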